	Assuming an average follow-up duration of 3 years, the study will require a minimum sample size of 9,600 adults. Assuming an average follow-up duration of 0.75 years, the study will require a minimum sample size of 36,485 adults.
	A feasibility analysis using the Medicare fee-for-service claims database estimated approximately 25 million adults are eligible for inclusion in the study during the years of interest.
Data analysis	Separate analyses will be conducted with 0 to 1 year and 0 to 3 years of follow-up. A cause-specific Cox proportional hazards model with time-varying covariates will be used for the primary analysis. The cause-specific cox model will be used to estimate hazard ratios (HRs) for each MACE outcome, comparing PCV13 vaccinated with PCV13 unvaccinated Medicare enrollees. The weighted cumulative incidence function (CIF) will also be presented, describing and accounting for competing risk events. The analysis will utilize Inverse Probability of Treatment Weighting (IPTW) to adjust for baseline differences between the vaccinated and unvaccinated cohorts. Covariates with residual imbalance after weighting will be included in the final models for further adjustment to control for potential confounders. The primary analysis models will also adjust for influenza vaccination status during follow-up as a time-varying covariate.
	The study will also include a mediation analysis, which is considered a secondary analysis. The mediation analysis will estimate the direct and indirect effects of PCV13 receipt on MACE, examining the extent to which the relationship between PCV13 and MACE within 1 year of follow-up is mediated by CAP. The mediation analysis will utilize the product method,  which uses a logistic weighted mediation model to assess the mediator and a Cox model weighted outcome model to derive the HR and confidence intervals (CI).
	The study will also include three sensitivity analyses. The first sensitivity analysis will incorporate the Fine-Gray model, which provides an alternative to the cause-specific Cox model and helps ensure the robustness of the findings when comparing different analytical approaches to competing risks. Second, the study will include a sensitivity analysis using an alternative definition of stroke. The primary analysis

CT24-WI-GL02-RF02 6.0 Non-Interventional Study Protocol Template For Secondary Data Collection Study Page 11 of 53

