# 8. RESEARCH QUESTION AND OBJECTIVES

Research question:

Is prior receipt of PCV13 associated with reduced risk of major adverse cardiovascular events (MACE) outcomes in adults aged  $\geq 65$  years?

The primary objective of this study is to:

1. Evaluate the effect of PCV13 receipt on the risk of major adverse cardiovascular events (MACE) at 1 and 3 years of follow-up among adults aged ≥65 years

The secondary objectives of this study are to:

PFIZER CONFIDENTIAL CT24-WI-GL02-RF02 6.0 Non-Interventional Study Protocol Template For Secondary Data Collection Study Page 15 of 53

- 1. Evaluate the effect of PCV13 receipt on the risk of myocardial infarction at 1 and 3 years of follow-up among adults aged ≥65 years
- 2. Evaluate the effect of PCV13 receipt on the risk of stroke at 1 and 3 years of follow-up among adults aged ≥65 years
- 3. Evaluate the effect of PCV13 receipt on the risk of hospitalization due to heart failure at 1 and 3 years of follow-up among adults aged ≥65 years
- 4. Examine the degree to which CAP mediates the relationship between PCV13 receipt and MACE at 1 year of follow-up among adults aged >=65 years

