# 9.3.4. Censoring

### Table 4.Censoring Variables

Variable	Role	Operational definition	Measurement period
Outcome under study	Censoring	See outcome table above. Table 2.	Follow-up
Disenrollment	Censoring	The month an individual disenrolls from the insurance plan, as indicated in the Master Beneficiary Summary File. Disenrollment date is calculated as the maximum date of enrollment.	Follow-up
Death	Censoring	Date of death reported in the database.	Follow-up
End of study period	Censoring	December 31, 2019	Follow-up
End of follow-up	Censoring	365 days after the index date for the 1- year analysis and 1095 days after the index date for the 3 year analysis.	Follow-up
PPSV23 receipt	Censoring	1 CPT or NDC code for PPSV23 vaccination during follow-up.	Follow-up
PCV13 receipt	Censoring	1 CPT or NDC code for PCV13 receipt during unvaccinated follow-up.	Follow-up
		1 CPT or NDC code for receipt of a second PCV13 vaccine during vaccinated follow-up.	

PFIZER CONFIDENTIAL

CT24-WI-GL02-RF02 6.0 Non-Interventional Study Protocol Template For Secondary Data Collection Study Page 26 of 53

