## 9.5. Study Size

To determine the appropriate sample size for our study, we conducted a power analysis based on logrank test. The analysis was designed to evaluate the effect of PCV13 vaccination on the risk of first event MACE, with the following key assumptions:

- Treatment-to-control group allocation ratio: Based on the feasibility study using data from September 14, 2014, to December 31, 2019, the proportion of the vaccinated group is 39.6%. Consequently, the treatment-to-control group allocation ratio was set to 2:3.
- Hazard ratio (HR): We assumed a hazard ratio of 0.85 for the vaccinated group compared to the unvaccinated group, indicating a 15% reduction in the risk of first event MACE associated with PCV13 vaccination. Another scenario with an HR of 0.8 is also provided.
- Hazard rate for control group: Based on the above feasibility study, the 5-year overall event probability was 21.2%. Consequently, we calculated the hazard rate for the control group to be 0.0507. This calculation was derived from the pre-assumed HR of 0.85, the overall 5-year survival probability, and the treatment-to-control group allocation ratio. For the scenario with HR=0.8, the corresponding hazard rate for the control group is 0.0518.
- Follow-up time: In this study, not all patients will complete the full duration of follow-up due to censoring events such as vaccination status switching or death. To account for this in the sample size calculation, we adjusted the calculation using shorter average follow-up periods. Specifically, we considered four follow-up durations: 1-year, 0.75 year, 3 years, and 2.75 years.
- Statistical power: 80%.
- Test was two-sided with significance level (α): 0.05, which corresponds to a 5% chance of a Type I error.

The required total sample sizes for each scenario were determined as follows to achieve a 80% power:

Hazard Ratio	Control Group Hazard Rate	Follow-up time in	Total N Required
		years	
0.85	0.0507	1	27,520
		0.75	36,485
		3	9,600
		2.25	12,585

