### 9.7. Data Analysis

The analyses will be conducted separately at 1 year and 3 years of follow-up.

Descriptive statistics will be used to summarize baseline characteristics by vaccination group before and after propensity score weighting. Categorical variables will be summarized using frequency counts and percentages. Continuous variables will be summarized using mean, standard deviation, median, 25th and 75th percentile, minimum, and maximum.

Detailed methodology for summary and statistical analyses of data collected in this study will be documented in a statistical analysis plan (SAP), which will be dated, filed, and maintained by the sponsor. The SAP may modify the plans outlined in the protocol; any major modifications of primary endpoint definitions or their analyses would be reflected in a protocol amendment.

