### **Primary Outcome Analysis**

The weighted cumulative incidence function (CIF) will be estimated to describe and account for mortality as a competing risk of MACE. This approach provides a non-parametric estimate of the cumulative incidence function, accounting for the competing risk events. The crude weighted CIF will be presented with the log-rank test to compare the CIF curve between the PCV13 vaccinated and PCV13 unvaccinated cohorts.

A cause-specific Cox proportional hazards model with a time-varying covariate for influenza vaccination status and a time-segment approach to PCV13 vaccination status will be used for the primary analysis. The cause-specific cox model will be used to estimate hazard ratios (HRs) for the first event of each MACE outcome, comparing PCV13 vaccinated with PCV13 unvaccinated Medicare beneficiaries. The model accounts for the possibility of competing risks by focusing on the cause-specific hazard. A time segment approach will be used to account for changes in PCV13 exposure status during follow-up, allowing adults who receive PCV13 during the study period to contribute a PCV13 unvaccinated and a PCV13 vaccinated time segment to the study.

For the any MACE outcome model, individuals are censored after experiencing their first MACE event during a given time segment, irrespective of whether the MACE event is myocardial infarction, stroke, or heart failure. The remaining models examine each type of MACE separately and experiencing one type of MACE event (i.e., myocardial infarction) is not a censoring criterion for the other types of MACE outcomes (i.e., stroke or heart failure) during a given time segment.

The HR for PCV13, with a 95% confidence interval, will be calculated over the follow-up period. If the proportional hazards assumption is violated—indicating the effect of PCV13 on the risk of MACE events changes over time—HRs will be estimated for specific follow-up periods (i.e., 0-1 years and 0-3 years).

[figure not shown]

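### The fallback for non-proportional hazards repeats the nested 0-1 and 0-3 year hazard ratios already planned, so it adds no estimate and never gives a later-period effect

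*Protocol*

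**What the plan says.** The primary objective in protocol section 8 concerns the effect of PCV13 "on the risk of major adverse cardiovascular events (MACE) at 1 and 3 years of follow-up among adults aged ≥65 years". Both horizons are analysed without any condition. The abstract states "Separate analyses will be conducted with 0 to 1 year and 0 to 3 years of follow-up", and section 9.7 opens with "The analyses will be conducted separately at 1 year and 3 years of follow-up". Table 4 ends follow-up "365 days after the index date for the 1- year analysis and 1095 days after the index date for the 3 year analysis".

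For the primary model, a cause-specific Cox regression, the Primary Outcome Analysis text says "The HR for PCV13, with a 95% confidence interval, will be calculated over the follow-up period". It reads a violation of proportional hazards as "indicating the effect of PCV13 on the risk of MACE events changes over time". The remedy it gives for that case is that "HRs will be estimated for specific follow-up periods (i.e., 0-1 years and 0-3 years").

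The only time-varying term in the primary model is influenza vaccination. The text names no period that starts after index, no PCV13-by-time term and no other time-dependent PCV13 effect. The same subsection plans a weighted cumulative incidence function (CIF) for each cohort, with death as a competing risk.

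**The concern.** A remedy for non-proportional hazards should describe how the effect differs between earlier and later follow-up. This one names the same two windows that are analysed anyway. One of its two results, the 0-3 year HR, is the single-coefficient summary whose assumption may just have failed.

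The interpretation of the 3-year result is at stake. An effect confined to year 1, a steady effect and an effect that reverses can all be summarised by a 0-3 year HR that does not tell them apart. The distinction matters here for two reasons. Section 9.7 names healthy-vaccinee behaviour as a possible source of residual confounding, and such bias need not be constant over follow-up. Section 7 designates the study a post-authorization safety study that might uncover an unanticipated safety signal, so an adverse effect after year 1 should not be averaged away.

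**Working it through.** **Step 1: compare the windows.**

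| Place in protocol | Condition | Windows |
|---|---|---|
| Abstract, Data analysis | none | 0-1 and 0-3 years |
| Section 8, primary objective | none | 1 and 3 years |
| Section 9.7, opening | none | 1 and 3 years |
| Table 4, end of follow-up | none | to 365 and to 1095 days after index |
| Section 9.7, Primary Outcome Analysis | proportional hazards violated | 0-1 and 0-3 years |

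The last row adds nothing to the others. Within each cohort both windows start at the same point and only the end differs, so 0-1 is contained in 0-3.

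**Step 2: inputs for an illustration.** Section 9.5 gives a control hazard of 0.0507 per year and states: "Consequently, the treatment-to-control group allocation ratio was set to 2:3", so the vaccinated share is 0.40. To reproduce the control hazard, solve 0.4(1 − exp(−5 × 0.85λ)) + 0.6(1 − exp(−5λ)) = 0.212, where 0.212 is the protocol's 5-year event probability and 0.85 its assumed HR. This gives λ = 0.0507, as stated.

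The remaining inputs are assumptions: the true HR in each period, no competing death, and a common censoring rate c of 0, 0.3 or 0.6 per year.

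**Step 3: the value the Cox HR estimates in large samples.** Let h(t) be the true HR at time t. The at-risk fractions are

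- vaccinated: S1(t) = 0.4 exp(−λ∫₀ᵗ h(u)du − ct)
- unvaccinated: S0(t) = 0.6 exp(−λt − ct)

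The single coefficient b fitted over 0 to T solves

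∫₀ᵀ [ S1 hλ − (S1 hλ + S0 λ) · S1 eᵇ / (S1 eᵇ + S0) ] dt = 0.

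| Assumed true HR | Fitted 0-1 | Fitted 0-3, c = 0 | c = 0.3 | c = 0.6 |
|---|---|---|---|---|
| 0.75 in year 1, then 1.00 | 0.75 | 0.913 | 0.887 | 0.861 |
| 0.80 in year 1, then 1.10 | 0.80 | 0.995 | 0.964 | 0.933 |
| 0.85 / 0.70 / 1.00 in years 1 / 2 / 3 | 0.85 | 0.848 | 0.836 | 0.829 |

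**Step 4: hand check of the first row.** The log of the 0-3 HR is close to the average of the period log HRs weighted by events. With no censoring, year 1 holds 32.6% of the events, so exp(0.326 × ln 0.75) = 0.910, against 0.913 from the equation. With c = 0.6, year 1 holds 53.1%, so exp(0.531 × ln 0.75) = 0.858, against 0.861. The true effects are the same in both cases. Only the censoring rate differs.

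**Step 5: reading the table.**

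- Row 1: the 1-3 year HR of 1.00 is never reported.
- Row 2: the 1-3 year HR of 1.10 is never reported, and the 0-3 HR is at or below 1.
- Row 3: the two reported HRs differ by at most about 0.02, although the true yearly HRs run from 0.70 to 1.00.

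**The case against.** Several points on the other side have force.

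- **A reader might infer that the two nested HRs can never reveal a changing effect.** That goes too far. A pair such as 0.75 and 0.913 visibly attenuates and hints at change. What stands is narrower: the hint is already in the planned output, it gives no later-period estimate, and it can be almost absent, as in row 3.
- **A reader might infer that a reported 3-year benefit would be false if it all arose in year 1.** The objective concerns risk at 3 years, which is cumulative. In row 1 without censoring, 3-year risk is 1 − exp(−0.0507 × 2.75) = 13.0% in the vaccinated and 1 − exp(−0.0507 × 3) = 14.1% in the unvaccinated, a ratio of 0.92. That is a true answer to the objective. It misleads only if presented as an effect that persists.
- **A reader might infer that waning is expected and that proportionality is almost sure to be rejected.** The protocol does not describe waning as expected, and it names no method for checking proportionality. About 25 million eligible adults would make a formal test very sensitive, but a graphical check is equally possible.
- **The weighted CIF is already planned.** Its curves would show descriptively whether the cohorts stop separating. It is not the stated remedy, however, and it gives no period-specific HR.
- **The windows in parentheses may be examples only.** The protocol uses i.e. loosely elsewhere, and detailed methods are left to a statistical analysis plan that is not at hand. This limits certainty about what will be run, but it does not make the two named windows a useful remedy.
- **Later-period HRs have their own weakness.** They condition on being event-free and uncensored at the start of the period. Baseline weighting does not guarantee balance among those who remain, and unvaccinated segments end at PCV13 receipt.

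**Conclusion.** The point holds as one of redundancy. The stated response to non-proportional hazards is the pair of nested analyses already planned without condition. It adds no estimate, leaves the effect after year 1 unestimated, and keeps a 0-3 year HR that mixes period effects in proportions set partly by censoring. The documents do not support the stronger readings that no change could ever be seen or that a 3-year risk reduction would be untrue.

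The size is illustrative. With identical true effects (0.75, then 1.00), the 0-3 HR moves from 0.913 to 0.861 as assumed censoring rises from 0 to 0.6 per year. With an assumed 0.80 then 1.10, it lies between 0.995 and 0.933. Both rest on the protocol's 0.0507 control hazard and 40% vaccinated, on assumed period HRs, and on no competing death and equal censoring in the two cohorts. The redundancy itself follows from the text and needs none of these assumptions. The change should be made before analysis.

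**What to change.** Replace the two windows in the parenthesis with disjoint follow-up periods, for example 0-1, 1-2 and 2-3 years, estimated from an exposure-by-period term in the weighted cause-specific Cox model. The exact cut-points are the sponsor's choice but should be fixed in advance. Finer cuts within year 1 would serve the 1-year analysis.

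From the weighted CIF already planned, report the difference between cohorts at 1 and 3 years with a confidence interval. It answers the cumulative-risk objective and does not need proportional hazards.

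State that HRs for later periods condition on remaining event-free and uncensored and should be read with that selection in mind, with inverse probability of censoring weights if these are used.

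The cost is one sentence in section 9.7, one model term and a few extra output rows, with no new data. Section 9.7 says that major modifications of the primary endpoint analyses would be reflected in a protocol amendment, so if the sponsor judges this change to be one, that is the route.

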### **Mediation** Analysis

The study will also include a secondary analysis to examine mediation. The mediation analysis will estimate the direct and indirect effects of PCV13 receipt on MACE, examining the extent to which the relationship between PCV13 and MACE within 1 year of follow-up is mediated by CAP. Direct (c') and indirect effects (a\*b) will be estimated. This analysis will employ the product method, which

PFIZER CONFIDENTIAL

CT24-WI-GL02-RF02 6.0 Non-Interventional Study Protocol Template For Secondary Data Collection Study Page 36 of 53 uses a logistic weighted mediation model to assess the mediator and a Cox model weighted outcome model to derive the HR and confidence intervals. Additionally, a counterfactual-based mediation analysis may be considered. This approach utilizes simulations to estimate the Controlled Direct Effect (CDE) and the Natural Indirect Effect (NIE), providing a comprehensive understanding of the mediation process. The mediation analysis will only adjust for influenza vaccination status during baseline. Further details on the mediation analysis will be provided in the SAP.

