### 7. RATIONALE AND BACKGROUND

Community-acquired pneumonia (CAP) is a major cause of morbidity and mortality in older adults. A systematic review conducted in 2020 reported that in the United States (US), the estimated annual incidence of hospitalized CAP among adults aged  $\geq 65$  years ranges from 847 to 3500 per 100,000 persons. In a prospective study of adults hospitalized with CAP conducted in Louisville, Kentucky during 2014 to 2016, 6.5% of patients died during hospitalization, and mortality increased to 30.6% at 1 year after hospitalization. CAP can be caused by a wide range of viral, bacterial, and fungal pathogens, with Streptococcus pneumoniae typically reported as a leading bacterial cause. In the Etiology of Pneumonia in the Community (EPIC) study conducted by the US Centers for Disease Control and Prevention (CDC) at 5 hospitals during 2010-2012, S. pneumoniae was the most common bacteria identified and the third most common pathogen overall, behind rhinovirus and influenza virus. A systematic literature review published in 2020 that included 146 studies evaluating CAP etiology in adults in developed countries found that S. pneumoniae remains the most common bacterial cause of CAP, despite some declines in incidence in recent years. Detection of pneumococcal CAP is underestimated using traditional diagnostic methods such as sputum culture, as evidenced by the EPIC study, which found that use of serotype-specific urinary antigen detection (ssUAD) assay that detects the serotypes included in the 13-valent pneumococcal conjugate vaccine (PCV13) substantially increased detection of pneumococcal pneumonia. The Louisville, Kentucky adult CAP study conducted ssUAD testing for 24 pneumococcal serotypes and found that 13% of patients had pneumococcal pneumonia. They estimated that each year in the United States, more than 225,000 adults are hospitalized for pneumococcal CAP, and one quarter of these patients die within one year after hospitalization.

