# 9.3.3. Mediation

### Table 3.Mediation Variables

Variable	Role	Operational definition	Measurement period
Community-acquired pneumonia (CAP)	Mediator	
 
≥1 ICD-9-CM or ICD-10-CM diagnosis code for CAP in any setting, where there were no hospital admissions or ventilator use within the 30 days prior.
 
CAP with be categorized as having 0 or ≥1 CAP event. Individuals will be classified as having ≥1 CAP event if there is at least one diagnosis code for CAP during one of the following time segments:
 
1. ≥0 days after the unvaccinated index date and before the minimum date of censoring for the unvaccinated time segment
 
2. ≥14 days after the vaccinated index date and before the minimum date of censoring for the vaccinated time segment.
 
ICD-9-CM and ICD-10-CM codes are listed in Annex 1.
 
	Follow-up
Community-acquired pneumonia (CAP) sensitivity	Mediator	
 
≥1 ICD-9-CM or ICD-10-CM diagnosis code for CAP in the hospital setting, where there were no hospitalizations or ventilator use in the 30 days prior the hospital admission associated with the CAP diagnosis.
 
For individuals with multiple CAP diagnosis codes during the 1-year follow-up period, CAP will be classified as the highest level of care associated with a CAP diagnosis code.
 
CAP with be categorized as having 0 or ≥1 CAP event. Individuals will be classified as having ≥1 CAP event if there is at least one diagnosis code for
 
	Follow-up

PFIZER CONFIDENTIAL

CT24-WI-GL02-RF02 6.0 Non-Interventional Study Protocol Template For Secondary Data Collection Study Page 25 of 53

CAP during one of the following time segments:

 
≥0 days after the unvaccinated index date and before the minimum date of censoring for the unvaccinated time segment
 

 
4. ≥14 days after the vaccinated index date and before the minimum date of censoring for the vaccinated time segment.
 

ICD-9-CM and ICD-10-CM codes are listed in Annex 1.

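### For a binary mediator with logistic and Cox models, the product a×b is not the indirect effect and overstates mediation through CAP at least 4-fold (secondary objective 4 only)

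*Protocol*

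**What the plan says.** The Abstract (Data analysis) commits to one approach: "The mediation analysis will utilize the product method". Section 9.7, Mediation Analysis, names the quantities: "Direct (c') and indirect effects (a\*b) will be estimated". It then says how the two models are built: the approach "uses a logistic weighted mediation model to assess the mediator and a Cox model weighted outcome model to derive the HR and confidence intervals". Table 3 in Section 9.3.3 makes the mediator binary: "CAP with be categorized as having 0 or ≥1 CAP event".

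A second approach, which would give a natural indirect effect by simulation, is optional: "Additionally, a counterfactual-based mediation analysis may be considered". The section ends with a deferral: "Further details on the mediation analysis will be provided in the SAP".

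The text does not define a or b and gives no formula that turns the logistic coefficient into a CAP probability. It states no expected effect of PCV13 on CAP or of CAP on MACE. Figure 2, the mediation diagram, is not reproduced in the copy at hand.

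**The concern.** A product of path coefficients equals an indirect effect when the mediator model is linear: a is then the change in the mediator itself, and b is the effect per unit of that mediator. Here the mediator model is logistic. On the natural reading, a is the change in the log odds of CAP, while b is the log hazard ratio for having CAP against not having it. Multiplying them treats one unit of log odds as if it were one whole case of CAP. The product is the same whether CAP affects 1 person in 100 or 1 in 3, although the amount of MACE that CAP can carry is very different in the two cases.

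Secondary objective 4 asks how much of the effect runs through CAP, so the size of the indirect effect is the answer to the objective. An estimator that is always too large would exaggerate the pneumonia pathway that Section 7 gives as the hypothesis. A very large cohort would not reveal the error; it would only narrow the interval around the wrong quantity.

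**Working it through.** The protocol states no mediation figure, so there is nothing of its own to reproduce.

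**Inputs from the protocol**
- Indirect effect a×b, logistic mediator model, Cox outcome model (Section 9.7); binary CAP (Table 3).
- Annual incidence of hospitalized CAP at age 65 and over (Section 7): "ranges from 847 to 3500 per 100,000 persons", that is 0.847% to 3.5%.
- Control hazard for MACE 0.0507 per year and assumed total hazard ratio 0.85 (Section 9.5). One-year control risk is 1 − exp(−0.0507) = 4.9%, so treating the outcome as uncommon is reasonable.

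**Inputs assumed here**
- PCV13-CAP odds ratio (OR) and CAP-MACE hazard ratio (HR).
- CAP risk in any setting, which is what the main mediator measures and for which no figure is given.

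**Formula.** Let p0 and p1 be the CAP risks without and with PCV13, with logit p1 = logit p0 + a. With an uncommon outcome and no exposure-mediator interaction:

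log NIE = ln[(1 − p1 + p1·e^b) / (1 − p0 + p0·e^b)]

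**A bound that needs no assumed effect sizes.** Write p = expit(x). Then ln(1 − p + p·e^b) = ln[(1 + e^(x+b)) / (1 + e^x)], and its derivative in x is expit(x+b) − expit(x). The logistic curve never has a slope above 1/4, so this derivative is at most |b|/4 in size. Over a range of length |a|, |log NIE| ≤ |a×b|/4. The raw product is therefore at least 4 times too large on the log scale, whatever the inputs.

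**One scenario in full** (p0 = 3.5%, OR 0.90, HR 3)
- Odds: 0.035/0.965 = 0.03627; times 0.90 = 0.03264; p1 = 0.03264/1.03264 = 3.161%.
- NIE HR = (1 + 2×0.03161)/(1 + 2×0.035) = 1.06322/1.07 = 0.994; log = −0.00636.
- a×b = ln 0.90 × ln 3 = −0.1054 × 1.0986 = −0.1158; exp(a×b) = 0.891.
- Ratio of logs: 0.1158/0.00636 = 18.2.
- Share of the assumed total effect, with ln 0.85 = −0.1625: 0.1158/0.1625 = 71% for a×b; 0.00636/0.1625 = 4% for the NIE.

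**Other assumed inputs**

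| CAP risk p0 | OR | HR | exp(a×b) | NIE HR | Ratio of logs |
|---|---|---|---|---|---|
| 0.847% | 0.85 | 2 | 0.894 | 0.999 | 90 |
| 3.5% | 0.90 | 2 | 0.930 | 0.997 | 22.3 |
| 3.5% | 0.85 | 3 | 0.836 | 0.990 | 18.7 |
| 10% | 0.85 | 5 | 0.770 | 0.961 | 6.5 |
| 30% | 0.85 | 3 | 0.836 | 0.959 | 4.2 |

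For CAP risks of 0.847% to 3.5%, OR 0.70 to 0.95 and HR 1.5 to 10, the ratio runs from about 10 to about 115.

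**Simulation check.** With 4 million subjects, p0 = 3.5%, OR 0.85, HR 3 and no direct effect, the total effect equals the indirect effect. The simulated HR was 0.993 (SE about 0.005). The formula gives 0.990, within one SE; exp(a×b) gives 0.836.

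**The case against.** **The meaning of a and b is inferred.** They are undefined in the text, the diagram is not shown, the cited method cannot be consulted, and details are deferred to the SAP, which may contain a binary-mediator formula. This limits certainty about what will be computed. It does not rescue the protocol text, which names a×b as the indirect effect, names the two models that would supply it, and leaves the natural indirect effect optional. A correct SAP formula would be repairing that statement.

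**The harm is contained.** The analysis is secondary, and the MACE, myocardial infarction, stroke and heart failure hazard ratios do not depend on it. The product has the right sign and is zero when the pathway is null, so only the size is wrong. All of this stands, but size is what objective 4 asks for.

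**The multiples are assumed.** This also stands. The 0.847% to 3.5% incidences are for hospitalized CAP, while the main mediator counts CAP in any setting. A reader might take 18-fold, or a range such as 6- to 90-fold, as a property of this study. The documents do not support any figure beyond the 4-fold minimum.

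**The formula is a simplification.** It treats CAP as fixed from the start with a constant hazard ratio, whereas Table 3 counts CAP over follow-up up to censoring. The value 0.994 is therefore a scenario result, not the true effect.

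**Two stronger readings fail.** A reader might infer that a×b would always credit CAP with most or all of the MACE effect. With OR 0.90 and HR 2 it gives (0.1054 × 0.6931)/0.1625 = 45%. A reader might also infer that the optional analysis is faulty because a controlled direct effect and a natural indirect effect do not combine to the total. Without exposure-mediator interaction, the controlled and natural direct effects coincide and the two do combine on the log scale. The protocol claims no decomposition in any case.

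**Conclusion.** The estimator is wrong as written and should be fixed; the consequence is confined to secondary objective 4. On the natural reading of a and b, raw a×b exceeds the log natural indirect effect at least 4-fold, always away from the null. That bound assumes the named logistic and Cox models, an uncommon outcome and no exposure-mediator interaction; it needs no assumed effect sizes. The contrast of 71% with 4% is an illustration that rests on an assumed odds ratio of 0.90, an assumed hazard ratio of 3 and a hospital-only CAP risk of 3.5%. The true multiple in this study cannot be derived from the protocol.

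**What to change.** In Section 9.7, Mediation Analysis, and in the matching Data analysis text of the Abstract:
- Remove raw a×b as the reported indirect effect.
- Define the indirect effect as the natural indirect effect for a binary mediator on the log-hazard-ratio scale, obtained from the closed form above or by simulation from the fitted mediator and outcome models. State the assumptions (uncommon outcome, no interaction) where the closed form is used.
- Make this analysis required rather than optional.
- Report the natural direct effect, the natural indirect effect and the proportion mediated, with bootstrap or delta-method intervals.
- Define any path labels that are kept, so that the text, Figure 2 and the SAP agree.

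The cost is a wording change and some computing time; no new data are needed. The reported mediated share will be smaller than raw a×b would have given. The change should be settled before results are seen.
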